The Immediate Extent of the Hypoalgesic Effect Following Central

Mobilisations to L3, L4 and L5.

October 27th 2023

Study Protocol

Study Design

The design of the study was a randomised, single-blind, repeated measures, cross-over design, performed in a single-centre environment. Ethical approval was gained from the School of Sport and Exercise Science ethics committee at the University of Worcester (ISES2018RF1). Informed consent was gained from each participant before testing.

Sample and Inclusion Criteria

The study included twenty asymptomatic participants (11 females and 9 males); the mean age of the participants was 21.9 years (±2.67, range 20- 30). A health questionnaire (based on the PARQ) was completed by each participant to establish any contraindications they may have to the experimental procedures, namely the application of vertebral mobilisations. No participants were required to be excluded as none of them had consulted their doctor in the last six months, were taking any medication, had an infection in the past two weeks, had no heart, asthma, diabetes, bronchitis, epilepsy or blood pressure issues, had any current muscle or joint injury, were able to train/exercise normally or knew of any other reason that would preclude them from participating.

Data Collection

Each participant was randomly assigned using a random number generator to the order in which their lumbar vertebral levels were mobilised and to the order of each dermatome level tested for the baseline and all three mobilisation interventions.

Before initiating the experimental procedure, the participant's age, height, and weight were recorded. The participant was instructed to lay on their back, on the plinth and had the five locations for dermatome testing marked with a water-soluble pen. The researchers utilised the method of using participant's finger breadth to establish dermatome testing sites (Gross et al 2015) the dermatome testing sites were based on Keegan and Garrett's dermatome map (Keegan & Garrett, 1948) see Figure 1. From this point forth, the spinal levels will be referred to as L2 or L3, respectively and the corresponding dermatome of the vertebral level will be referred to as DL2 or DL3.

Figure not included due to copyright reasons.

Figure 1. The dermatome map was established originally by Keegan & Garrett (1948). DL2 landmark-4 participant's finger breadth inferior from ASIS, mid anterior thigh. DL3 landmark-8 participant's finger breadth inferior from DL2 landmark, mid anterior thigh. DL4 landmark- 2 participant's finger breadth superior from the proximal border of the patella, mid-way. DL5 landmark- 4 participant's finger breadth inferior from tibial tuberosity, then 1 participant's finger breadth lateral (so that the landmark is on the tibialis anterior, not tibia). S1 landmark- 1 participant's finger breadth inferior to the lateral malleolus. Adapted and used with permission from Anatomical Record. 1948;102(4):409.

Once these locations were marked on the participant's left leg, a demonstration of the Neuropen® (Owen Mumford, Oxfordshire, UK) was performed on the participant's hand (opposite to the side being tested). Once all this had been completed, baseline measures were taken. Using the Neuropen®, a standardised force of 40g was applied to one of the locations. The participant then received a small piece of card with a vertical 10cm visual analogue scale (VAS) line on it and a pen and was asked to "draw a horizontal line on the scale to indicate how much sensation you feel, 0 being can-not feel anything and 10 being an extremely strong sensation". Following this explanation, the participant was asked if they understood and whether they needed further instruction to complete the VAS card. Once the participant marked the card, the card and pen were collected and stored, this process was repeated with the remaining four locations (these five cards provided the baseline data). A new tip was used for each participant, and a decrease in PPS represents a reduction in pain.

Once baseline measurements were collected by the lead researcher, the participant was asked to turn onto their front; the first (pre-determined) lumbar vertebra was found using the iliac crest as an anatomical landmark for the differentiation test. When the correct vertebra was located, the experimenter pressed record on the laptop connected to the PGD plinth (see Cooper et al (2018) for full details) to record the force applied and calculate the frequency.

The lumbar vertebra was mobilised using Maitland's vertebral mobilisation method for posterioranterior central vertebral pressures (PACVPs) for four sets of 30 seconds (Pentelka et al 2012) with up to 30s between each, at a grade III amplitude (Maitland et al 2005) and a target rate of 3Hz (Piekarz & Perry 2015) to ensure the total time for testing was less than fifteen minutes in duration, before the opioid system is activated (Beatti et al 2010). Once the fourth 30-second mobilisation had been completed, the researcher pressed stop on the laptop and asked the participant to roll onto their back. Then the next five sets of data were collected following the same procedure implemented for the baseline measures (collected in a different, pre-determined order each time). This process was repeated for the remaining two vertebrae.

Statistical Analysis Plan

A Multivariate Analysis of Variance (MANOVA) for individual levels against baseline and a One-way Analysis of Variance (ANOVA) for the collated (data set reduced to identify effects at either the same vertebral level as treated versus baseline, one, two or three above or below respectively) mobilisation effect including Tukey post hoc tests for both were conducted using IBM SPSS statistics 25, p values less than 0.05 were defined as acceptable. Effect sizes identifying Cohens d (Large 0.8, Medium 0.5, and Small 0.2) and Magnitude Based Inferences (MBI) were also calculated for each a more comprehensive analysis of the data.

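### No balancing of the level orders is described and no session-position term is planned, so any session drift adds avoidable chance error to the level comparisons

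*Combined protocol and SAP*

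**What the plan says.** The Study Design section calls the trial a "randomised, single-blind, repeated measures, cross-over design", and the title gives the treatments as "Mobilisations to L3, L4 and L5". Twenty people took part.

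Under Data Collection, level order comes from a random number generator: "Each participant was randomly assigned using a random number generator to the order in which their lumbar vertebral levels were mobilised". The same sentence extends the randomisation "to the order of each dermatome level tested for the baseline and all three mobilisation interventions". No block, Latin square, quota or list of sequences is mentioned. The text does not say that the draw was unrestricted either. The first vertebra is described as fixed in advance, and the site readings after each mobilisation are "collected in a different, pre-determined order each time".

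On timing: "Once baseline measurements were collected by the lead researcher, the participant was asked to turn onto their front". One level is then mobilised and the five sites are re-tested. After that, "This process was repeated for the remaining two vertebrae". No washout and no fresh baseline are described.

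The Statistical Analysis Plan sets out a MANOVA of individual levels against baseline and a one-way ANOVA of data collated by distance from the treated level. Tukey tests follow both. No term for participant, period, sequence or position is named.

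**The concern.** Each person gives 20 pinprick ratings (five sites at baseline and after each of three mobilisations). Ratings may move over such a series through habituation, sensitisation or carry-over. In a cross-over this is handled by spreading the treatments evenly over the positions, by fitting position in the model, or both. The plan describes neither.

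If one level happens to sit later in the session than another, part of any drift shows up as a difference between those levels. The study asks how far along the limb an effect extends, so noise in comparisons between levels and between distances bears on its question. It would also carry into any Cohen's d or magnitude-based inference computed from those contrasts.

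**Working it through.** The plan gives no balance, power or drift figure, so there is nothing of its own to reproduce.

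**Inputs from the documents.** 20 participants; three levels, hence 3! = 6 orders; five sites (DL2, DL3, DL4, DL5, S1); one baseline, always first.

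**Assumptions.** An unrestricted draw over the six orders; linear drift of d within-person SDs per position, with d = 0.25, 0.5 and 1.0 because the documents give no value; independent normal errors with within-person SD 1. Carry-over is not modelled.

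**1. How uneven the orders would be** (multinomial, 20 people)
- First-position counts of the three levels differ by 4 or more in 61% of draws, and by 6 or more in 29%.
- At least one of the six orders is never used in 15%.
- The most even split possible (4, 4, 3, 3, 3, 3) arises in 1.3%.

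**2. Gap in mean position between two levels.** Within a person the difference in position is ±1 with probability 2/3 and ±2 with probability 1/3. Its variance is (2/3)(1) + (1/3)(4) = 2. Over 20 people the SD of the mean gap is √(2/20) = 0.316. For a given pair the gap is 0.5 or more in 13% of draws.

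**3. Effect on a level-versus-level contrast, no position term.** Error variance of the paired mean difference is 2/20 = 0.100. Drift adds d² × 2/20. The total is 0.100 × (1 + d²).

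| d | Typical leak, 0.316d | Variance | Increase | SD by formula | SD simulated |
|---|---|---|---|---|---|
| 0.25 | 0.08 | 0.106 | 6% | 0.326 | 0.326 |
| 0.5 | 0.16 | 0.125 | 25% | 0.354 | 0.353 |
| 1.0 | 0.32 | 0.200 | 100% | 0.447 | 0.449 |

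With the most even split instead, the simulated SD stays between 0.318 and 0.330 over the same drifts.

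**4. Bias or noise?** Over 20,000 simulated trials per setting, mean bias in the L3 versus L5 contrast was at most 0.005, and the type I error of a paired test at two-sided 0.05 was 4.8% to 5.4%. The leak is fixed once the orders are drawn, but averages to zero over draws.

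**5. With participant, level and position fitted.** Unrestricted orders inflate the contrast variance by about 5.8% on average, whatever the common drift. On the standard error this is √1.058 = 1.029, or 2.9%. The term pays for itself when 1 + d² exceeds 1.058, that is when d exceeds √0.058 = 0.24. A list of six orders three times each plus two more reduces the cost to 0.25% to 0.5%, averaged over the three contrasts.

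**6. Which collated categories are exposed**
- Same level: L3–DL3, L4–DL4, L5–DL5.
- One above: L3–DL2, L4–DL3, L5–DL4.
- One below: L3–DL4, L4–DL5, L5–S1.
- Two above: L4–DL2, L5–DL3. Two below: L3–DL5, L4–S1.
- Three above: L5–DL2. Three below: L3–S1.

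The first three categories take one reading from every level in every person, so they cover all three positions and common drift cancels between them. The two- and three-level distances do not.

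**7. Level versus baseline.** Baseline is at position 0 and each level averages position 2, so drift biases the contrast by 2d (0.5, 1.0 and 2.0 SD). False rejection was about 32%, 82% and over 99% with unrestricted orders, and 32%, 83% and 100% with balanced ones. Order balance makes no difference here.

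**The case against.** The strongest reply is that unrestricted randomisation is an inference. A random number generator can shuffle a balanced list, and orders fixed in advance fit a prepared list just as well. This stands: every probability above is conditional, and the plan is silent on the method rather than known to be at fault.

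A second reply is that chance imbalance in a randomised order is not bias. This stands too. A reader might infer that the level comparisons are systematically biased or that false positives are inflated. The calculation does not support that for a paired test. It does not vouch for the ANOVA as written, since the plan names no participant term.

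Third, the drift is unknown. At d = 0.25 the typical leak is only 0.08 SD, and the position term roughly breaks even.

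Fourth, the study is reported as finished, so orders cannot be reassigned. Once position is fitted, little of the allocation problem is left. That is correct, and it makes the model term the remedy for these data.

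What the replies leave untouched is that nothing in the plan ensures balance and nothing in the analysis adjusts for its absence.

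**Conclusion.** The point holds as a matter of precision and reporting. If the orders were drawn freely, imbalance at n = 20 is likely. The planned analysis would then carry 6% to 100% extra variance in level-versus-level contrasts for assumed drifts of 0.25 to 1.0 within-person SD per position. This rests on linear drift common to all participants, independent errors and no modelled carry-over. It is worth acting on, but does not by itself invalidate the study.

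Three wider readings are tempting and are not supported:
- **That drift contaminates the whole collated analysis.** Comparisons among same level, one above and one below are protected from level-order drift; only the two- and three-level distances are exposed.
- **That balancing the orders would deal with session drift.** It would not touch the comparisons with baseline, where the larger problem lies.
- **That the site-testing order causes comparable harm.** The figures here concern level order only, and no harm from random site order has been shown.

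**What to change.** **For this study.** State how the orders were generated. Report how many participants had each of the six orders. Fit participant and session position (1, 2, 3, as categories) among the three post-mobilisation readings, for the level contrasts and for the collated distances. Baseline should stay out of the position term, since its position never varies. This uses information that should already be on record. It costs some analysis time and about 6% of variance on average if the draw was unrestricted. If a balanced list was in fact used, one sentence and the counts close the allocation part.

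**For any repeat study.** Use each of the six orders three times, plus two further orders that start with different levels, so that first-position counts are 7/7/6. Put the list in random sequence, prepare it in advance and conceal it. The only cost is slightly more predictable orders. Keep the position term as well. With the most even allocation and no such term, drift stays in the error estimate, and the paired test rejected in only 4.2%, 3.1% and 0.9% of null trials at d = 0.25, 0.5 and 1.0.

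**In both cases.** State that neither change separates level-versus-baseline effects from time in the session.

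### One baseline card per site is the comparator for all three mobilisations: a second baseline round, analysed within person, would sharpen contrasts with baseline (optional refinement)

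*Combined protocol and SAP*

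**What the plan says.** Study Design describes a "randomised, single-blind, repeated measures, cross-over design". Under Sample and Inclusion Criteria, "The study included twenty asymptomatic participants". The title gives the conditions as "Mobilisations to L3, L4 and L5".

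Data Collection describes one Neuropen stimulus and one VAS card at each of five sites (DL2, DL3, DL4, DL5, S1) before the first turn to prone, and says that "these five cards provided the baseline data". After a vertebra is mobilised, the same five sites are tested once more. Then "This process was repeated for the remaining two vertebrae". No repeat reading at baseline and no new baseline between mobilisations is described.

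The Statistical Analysis Plan names a MANOVA "for individual levels against baseline" and a one-way ANOVA on readings collated by distance from the treated level (same level, or one to three above or below), both with Tukey post hoc tests. Cohen's d and magnitude-based inferences are added. The plan does not mention a within-person term, reading reliability, or the dependence that a common comparator creates.

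**The concern.** Each participant gives 15 post-mobilisation readings (3 levels × 5 sites), and all are compared with five single readings. The random error of a baseline card therefore enters three changes in the same direction. A card that happens to read high at DL4 makes DL4 look less sensitive after L3, after L4 and after L5. In the collated analysis it does so at one below, same level and one above.

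Two things are at stake. The first is precision: the comparator is read no more often than each condition, although every comparison with baseline depends on it. The second is interpretation: the study asks about the extent of hypoalgesia, and a reader may take agreement between levels or adjacent distances as mutual support when part of it is one card's error.

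The point concerns random reading error only. That baseline always comes first, with possible drift or habituation, is a separate matter that extra baseline cards would not solve.

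**Working it through.** The plan states no sample-size calculation, SD, reliability or target effect, so there is no figure of its own to reproduce.

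**Inputs from the documents.** n = 20; 3 levels; 5 sites; 1 baseline card and 3 post cards per site; alpha 0.05.

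**Assumptions.** Two-sided tests. Independent reading error with within-person SD σ; baseline/post error variance ratio r = 1, range 0.5 to 2. Each post reading is compared with its own site's card, which the SAP does not specify.

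**1. What each card serves** (L3, L4, L5 mobilised in turn)

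| Site | Distances |
|---|---|
| DL2 | 1, 2, 3 above |
| DL3 | same, 1 above, 2 above |
| DL4 | 1 below, same, 1 above |
| DL5 | 2 below, 1 below, same |
| S1 | 3, 2, 1 below |

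**2. Variance of a change.** With k baseline cards averaged, Var = σ²(1 + r/k).
- r = 1: 2.0σ² for k = 1 and 1.5σ² for k = 2. SE ratio √(1.5/2.0) = 0.866, a 13% fall, equivalent to 20/0.75 = 26.7 people for these contrasts.
- Baseline card's share at k = 1 is r/(1 + r): 33% at r = 0.5, 50% at r = 1, 67% at r = 2.
- If half the baseline error is shared within the occasion, averaging two cards leaves 0.5 + 0.5/2 = 0.75, so Var = 1.75σ² and the SE ratio is √(1.75/2) = 0.935, a fall of about 6%.

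**3. Correlation of two changes at one site.** (r/k)/(1 + r/k). With r = 1: 0.50 for k = 1 and 0.33 for k = 2.

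**4. Correlation between distance means** (r = 1, k = 1). Same level uses DL3, DL4 and DL5; one above uses DL2, DL3 and DL4; they share two cards. Covariance 2σ²/9, each variance 6σ²/9, correlation 2/6 = 0.33. The same method gives 0.41 for one against two, 0.35 for two against three, 0.20 for same against two, and 0 for same against three.

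**5. Power of a paired t test** (noncentral t, df 19, two-sided 5%, r = 1), one card to two: 56% to 68% at a true change of 0.7σ; 67% to 79% at 0.8σ.

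**6. Clustering with no true effect** (simulated unadjusted paired tests, n = 20)

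| | One card | Two cards | Separate baselines |
|---|---|---|---|
| Second false positive at a dermatome, given one | 16% | 10% | 5% |
| Two or more at a dermatome | 2.0% | 1.3% | 0.8% |
| Any at a dermatome | 12.8% | 13.5% | 14.4% |

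Each single test stays at 5%.

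**7. The SAP's one-way ANOVA with Tukey, read literally** (simulated on raw readings, 4 groups of 20, true change 0.7σ). Power for the contrast with baseline, one card to two averaged cards, by assumed between-person variance:
- 0: 34% to 39%
- 0.5σ²: 17% to 18%
- σ²: 8.1% to 7.6%
- 2σ²: 1.9% to 1.8%

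**The case against.** A shared baseline is ordinary when several conditions are compared with one control, and Tukey allows for a common comparator within one ANOVA. That stands for the error rate. Tukey does not restore precision, does not remove the 0.50 correlation, does not connect the level and distance analyses, and does not cover Cohen's d or magnitude-based inferences.

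The strongest objection is that the power gain in step 5 belongs to a paired test that the SAP does not name. This stands: step 7 shows almost no gain, or a slight loss, once people differ. Extra cards pay only if the analysis uses the pairing.

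Three stronger readings are tempting, and the documents support none of them:
- *The single card hurts every planned comparison, and the baseline ought to have about √3 times the readings of a condition.* Tukey covers all pairs. Level-versus-level contrasts at a site do not use the baseline card, and the √3 rule is optimal only when comparisons with control are all that matter.
- *The shared card produces a false picture of wide extent.* Each dermatome has its own card, so a high DL4 card does not lower DL2, DL3, DL5 or S1. The linkage fades to 0.20 and then 0 as distance from the treated level grows.
- *It inflates false positives.* The 16% is conditional on a first false positive. Two or more at a dermatome occur in 2.0% of null trials, and the chance of any is slightly lower with the shared card.

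Time is a fair objection too. Four 30-second sets with three rests of up to 30 seconds take up to 3.5 minutes, so three levels take up to 10.5 minutes before cards, turning and palpation. The protocol's fifteen-minute limit does not say whether baseline counts.

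**Conclusion.** The concern holds in a limited form. In a within-person analysis, one single-stimulus card per site is a large part of the error of every change from baseline and ties together results that a reader could take as separate. It does not bias the average effect. The direction follows from the design; the size rests on test-retest error that the documents do not give. The 13% is therefore an upper figure under equal, independent error, not an expected gain; a noisier baseline (r = 2) would gain more and a cleaner one (r = 0.5) less. The distance correlations also depend on pairing each reading with its own site's card. The plan is not invalid without this change, so it ranks as an optional refinement.

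**What to change.** For a repeat of the study, or if collection is still open:
- Take two complete baseline rounds of five cards, each in its own random site order, before the first turn to prone.
- Enter both rounds as the comparator in a repeated-measures or mixed model with participant as a factor, replacing the one-way ANOVA on raw readings. The two changes belong together.
- Report the test-retest SD from the two untreated rounds, which the plan currently lacks.

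Cost: 25 cards per participant instead of 20, five more stimuli, a few minutes, and a rewritten analysis paragraph. If the fifteen-minute limit runs from baseline, part of it is used, so the protocol should first say where the limit starts.

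The document is in the past tense, so collection may be finished. In that case no cards can be added. The within-person model can still be used, and the report should carry one sentence saying that level and distance effects share a single baseline card per site, so agreement between them is not independent confirmation.

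### The only baseline always comes first and no wash-out or period term is described, so drift can read as effect and lingering local effect as spread

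*Combined protocol and SAP*

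**What the plan says.** Study Design calls the trial a randomised, repeated-measures cross-over. Data Collection randomises two things: the order in which L3, L4 and L5 are mobilised, and the order in which the five sites are tested.

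Baseline is a single round: "this process was repeated with the remaining four locations (these five cards provided the baseline data"). The participant then turns over and "the first (pre-determined) lumbar vertebra was found using the iliac crest" as a landmark. After mobilisation the five sites are retested, "collected in a different, pre-determined order each time". Then "This process was repeated for the remaining two vertebrae". The only gap given is up to 30 seconds between sets within one mobilisation. A limit of under fifteen minutes on total testing time is mentioned, without saying whether it applies per level or per session.

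The Statistical Analysis Plan names two analyses. The first is "A Multivariate Analysis of Variance (MANOVA) for individual levels against baseline". The second is a one-way ANOVA on a collated data set, described as "data set reduced to identify effects at either the same vertebral level as treated versus baseline, one, two or three above or below respectively". Both carry post hoc comparisons: "including Tukey post hoc tests for both were conducted using IBM SPSS statistics 25". Cohen's d, with benchmarks of 0.2, 0.5 and 0.8, and magnitude-based inferences (MBI) are added. No period, sequence or prior-mobilisation term is named.

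**The concern.** The title asks how far the hypoalgesic effect extends. The plan answers by comparing levels, and distances from the treated level, with baseline. Two things other than mobilisation could produce the same pattern.

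- **Drift.** The outcome is a subjective rating given 20 times per person (4 rounds of 5 sites). If ratings fall with repetition, every site looks hypoalgesic. If they rise, a real effect is hidden. Baseline is always round one, so comparing with baseline is also comparing with an earlier time.
- **Carry-over.** DL3, DL4 and DL5 serve as the same-level site in one round and as a neighbouring site in the others. A local effect that outlasts its own round is then counted as an effect one or two levels away, which is what the study sets out to measure.

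The word cross-over invites readers to treat change from baseline as a randomised comparison. It is not one.

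**Working it through.** The plan gives no sample-size, drift or persistence figure, so there is nothing of its own to reproduce. Inputs from the documents: 20 participants, 3 levels (6 possible orders), 5 sites, one baseline round placed first. Sizes of drift, carry-over and variance shares below are assumptions.

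**1. Can a period term rescue the baseline contrast?** Code one indicator for each level and one for each of rounds 1 to 3 after baseline. In every row the three level indicators sum to the same value as the three round indicators: 0 at baseline, 1 otherwise. So mobilised-versus-baseline is aliased with time. With the six orders as blocks, the design matrix has rank 11 for 12 columns; with prior-level terms added, rank 13 for 15. L3 versus L4 is estimable; L3 versus baseline is not.

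**2. Size of drift.** If linear at δ per round, the mean shift from baseline is (δ + 2δ + 3δ)/3 = 2δ at each level and distance, on average over orders. A single step of δ after baseline, then a plateau, gives δ. If d is standardised by the single-reading SD (the plan gives no denominator), linear drift of 0.10, 0.25 or 0.40 SD per round gives d = 0.2, 0.5 or 0.8 with no treatment effect.

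**3. What randomisation protects.** Every round supplies one same-level and two one-off readings, whichever level is treated, so common drift cancels exactly between those classes. Two-off and three-off readings number 1 and 1 for L3 or L5, but 2 and 0 for L4, so there, and between levels, it cancels only on average.

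**4. Carry-over.** Let a fraction c of a purely local effect of size 1 remain per round. For a given treated level, another level was mobilised one round earlier in 1/3 of orders and two rounds earlier in 1/6. A site whose own segment is mobilised in the study therefore carries c/3 + c²/6 on average. Such sites make up 4 of the 6 one-off treated-level/site pairs, 2 of the 4 two-off pairs and neither of the 2 three-off pairs.

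| c | One off: (2/3)(c/3 + c²/6) | Two off: (1/2)(c/3 + c²/6) | Three off | Same minus one-off (true 1) |
|---|---|---|---|---|
| 0 | 0 | 0 | 0 | 1 |
| 0.25 | 0.063 | 0.047 | 0 | 0.94 |
| 0.5 | 0.139 | 0.104 | 0 | 0.86 |
| 1 | 0.333 | 0.250 | 0 | 0.67 |

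The values are the same above and below the treated level.

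**5. P-values.** The plan does not state pairing, unit of analysis or pooling of above with below. In simulation with unpaired Tukey tests on participant means and pooled classes, drift of 0.10 SD per round flags a given class in at most about 2% of runs. With a paired test on participant means (Bonferroni over 10 contrasts; between-participant share of variance 0.2 to 0.8, assumed), the one-off class is flagged in about 11–54% of runs. A closed-form check agrees. The shift is 0.20, and the variance of a person's change is (1/6 + 1/5)(1 − share). The standard error with 20 people is then 0.121 at share 0.2 and 0.061 at share 0.8, so the expected t is about 1.65 or 3.30 against a critical value of 3.17. Power is about 9% or 56%.

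**6. First mobilisation only.** With independent reading errors (assumed), interval widths relative to the full data are:
- same level: √(60/20) = 1.73;
- one-off: √[(1/2 + 1/2)/(1/6 + 8/36)] = 1.60;
- two-off: √(1.667/0.5) = 1.83;
- three-off: √3 × 2.179/2.093 = 1.80, because only about 13 people contribute.

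By level, about 7 people remain: half-width t(6)/√7 = 0.92 SD of change, against t(19)/√20 = 0.47.

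**7. Modelling carry-over.** A noiseless least-squares fit was run for 18 people (3 per order), with participant-by-site effects, distance and period, with and without same-segment lag-1 and lag-2 terms. The target is same minus one-off.

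| Assumed effect | True | Without lags, c = 0.25, 0.5, 1 | With lags, c = 0.25, 0.5, 1 |
|---|---|---|---|
| Purely local | 1.00 | 0.91, 0.79, 0.50 | 1.00, 1.00, 1.00 |
| Graded (1; 0.5 one off; 0 beyond) | 0.50 | 0.45, 0.40, 0.25 | 0.54, 0.60, 0.77 |

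The lag terms raise the standard error from 0.175 to 0.260, about 1.5 times.

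**The case against.** The best defence is that order was randomised, the session was kept short on purpose, and nothing shows that ratings drifted or that effects lingered. Part of this stands. Randomisation does protect between-level and between-class contrasts from common drift. At c = 0 there is no carry-over. The analysis section is one short paragraph, so the fair statement is that it names no period term, not that none was fitted.

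Four stronger readings are tempting, and the documents do not support them.

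- A reader might infer that the observed effects are artefacts. No size or direction is given for drift, and no size for persistence.
- A reader might infer from the fifteen-minute limit that no wash-out was possible. Three mobilisations take 6 to 10.5 minutes (3 × 4 × 30 seconds, plus up to three 30-second gaps each). That leaves 4.5 to 9 minutes if the limit covers the session. It may instead apply per level.
- A reader might infer that only Cohen's d and MBI are affected and the p-values are safe. That depends on unstated choices: it is roughly true for unpaired participant means at small drift, and untrue for a paired test.
- A reader might infer that lag terms solve carry-over. They do so only for a purely local effect. With the graded effect assumed above and c = 0.5, the model without lags understates the contrast by 21% and the model with lags overstates it by 21%. An extent study cannot assume a purely local effect.

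None of this protects the baseline contrasts on which both analyses rest.

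**Conclusion.** The concern holds. Contrasts with baseline are before-after comparisons that no analysis of these data can separate from time. The distance classes also absorb any local effect that lasts beyond its own round. Under linear drift the bias is 2δ everywhere; under a single step it is δ. Under geometric persistence of a purely local effect, the false effect reaches at most one third of the local effect one level away and one quarter two levels away, and is nil three levels away. These sizes are conditional on assumptions that the documents neither confirm nor exclude. Effect sizes and MBI carry the bias directly. P-values can carry it too, to a degree that cannot be fixed until pairing, unit of analysis and pooling are stated. This matters enough to act on, because it changes what the study can claim about extent.

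**What to change.** 1. Describe all level-versus-baseline and distance-versus-baseline results, including Cohen's d and MBI, as uncontrolled before-after change. Say that a period term cannot separate mobilisation from drift when baseline is always first.
2. Report change from baseline after the first mobilisation only, by distance class, as a sensitivity analysis. It removes carry-over whether the effect is local or spread, but not drift. By level, treat it as descriptive only.
3. Optionally, as secondary, add a within-participant, within-site analysis of the post-mobilisation readings with distance, period and same-segment prior-mobilisation terms. State that it is unbiased only for a purely local effect. Show it with and without the lag terms, beside the first-round result.
4. Report the actual interval between levels, and whether the fifteen-minute limit applies per level or per session.
5. State whether tests are paired, the unit of analysis, and whether above and below are pooled.

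The text is in the past tense, so the design cannot change. The cost is SAP wording and re-analysis of readings already held using the recorded orders. Class intervals in item 2 are about 1.6 to 1.8 times wider if errors are independent, and less if a person's change is shared across sites. The claim about change from baseline becomes more modest.
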